15.0 STATISTICAL SOFTWARE

Statistical analyses will be performed using version 9.4 (or newer) of SAS® on a UNIX operating system.

16.0 DATA HANDLING CONVENTIONS

16.1 VISIT TIME WINDOWS

Table 16-1 presents the visits assigned for efficacy and safety analyses and the corresponding range of treatment days (window) during which an actual visit may occur.

Table 16-1 Visit Time Windows

Derived Visit	Open-label Period	
	Scheduled Visit Day Relative to the first dose of OL IP	Window
OL Baseline	Day 1	Days \leq 1
OL Week 1	Day 8	Days [2, 11]
OL Week 2	Day 15	Days [12, 18]
OL Week 3	Day 22	Days [19, 25]
OL Week 4	Day 29	Days [26, 35]
OL Week 6	Day 43	Days [36, 49]
OL Week 8	Day 57	Days [50, 63]
OL Week 10	Day 71	Days [64, 77]
OL Week 12	Day 85	Days [78, 91]
OL Week 14	Day 99	Days [92, 105]
OL Week 16	Day 113	Days [106, 119]
OL Week 18	Day 127	120 \leq days \leq the day of the last visit during the OL period*
End of the OL Period ^a	Last Assessment during the OL	
Double-blind Period		
	Scheduled Visit Day Relative to the first dose of DB IP	Window
	Day 1	Days \leq 1
DB Baseline (for efficacy endpoints only)	Day 15	Days [2, 21]
DB Week 2	Day 29	Days [22, 35]
DB Week 4	Day 43	Days [36, 49]
DB Week 6	Day 57	Days [50, 63]
DB Week 8	Day 71	Days [64, 77]
DB Week 10	Day 85	Days [78, 91]
DB Week 12	Day 99	Days [92, 105]
DB Week 14	Day 113	Days [106, 119]

Derived Visit	Open-label Period	
	Scheduled Visit Day Relative to the first dose of OL IP	Window
DB Week 18	Day 127	Days [120, 133]
DB Week 20	Day 141	Days [134, 147]
DB Week 22	Day 155	Days [148, 161]
DB Week 24	Day 169	Days [162, 175]
DB Week 26	Day 183	176 ≤ days ≤ the day of the last visit during the DB period
End of the DB period^a	Final or Termination Visit during the double-blind treatment period	
	Safety-follow-up (SFU) Period^b	
	Scheduled Visit Day Relative to the start of SFU	Window
SFU Week 2 ^b	Day 15	+1 ≤ days ≤ 21
SFU Week 4 ^b	Final or Termination Visit of the study after day 21 .	

OL Day 1 = the date of the first dose of open-label investigational product;

DB Day 1 = the date of the first dose of double-blind investigational product. There is no Day 0.

a Presented in analysis tables for safety parameters, including but not limited to electrocardiograms, clinical laboratory values, and vital signs.

b Presented in analysis tables for vital signs.

OL = Open Label; DB = Double-blind; SFU = Safety Follow-up; ET = Early Termination; IP = Investigational Products.

* All the available OL week 18/visit 13 Ophthalmological examination will be mapped to the OL safety period.

If a patient has 2 or more visits within the same window, the last visit with a non-missing value will be used for analysis.

16.2 DERIVED EFFICACY VARIABLES AND SAFETY VARIABLES

If only a few item scores are missing, the total score will be calculated based on available item scores using the following formula: (total number of items in the scale) × (sum of non-missing items / number of items with non-missing values). The maximum number of missing items allowed for the total scores imputation is specified below.

Structured Clinical Interview for the Positive and Negative Syndrome Scale Total Score

The total score is derived as the sum of the 30 items (P1-P7, N1-N7, and G1-G16) of the Structured Clinical Interview for the Positive and Negative Syndrome Scale (SCI-PANSS). If more than 3 items for the SCI-PANSS total score are missing, then the total score will be set to missing.

Structured Clinical Interview for the Positive and Negative Syndrome Scale Positive Score

The score is the sum of the 7 items (P1-P7) of the SCI-PANSS. If any item for the SCI-PANSS positive score is missing, the respective score will be set to missing.

Structured Clinical Interview for the Positive and Negative Syndrome Scale Negative Score

The score is the sum of the 7 items (N1-N7) of the SCI-PANSS. If any item for the SCI-PANSS negative score is missing, the respective score will be set to missing.

PANSS factor score for negative symptoms

The score is the sum of questions N1, N2, N3, N4, N6, G7, and G16. If any sub item is missing, the PANSS factor score for negative symptoms will be missing.

PANSS factor score for positive symptoms

The score is the sum of questions P1, P3, P5, P6, and G9. If any sub item is missing, the PANSS factor score for positive symptoms will be missing.

PANSS Responder

PANSS responder is defined as patients with 30% or more improvement in PANSS total score relative to baseline.

Abnormal Involuntary Movement Scale Total Score

The total score is the sum of the first 7 items of the AIMS. If more than 1 item for the AIMS (items 1-7) is missing, then the total score will be set to missing. Items 8 through 12 will be summarized separately

Simpson-Angus Scale Total Score

The total score is the sum of the 10 items of the SAS. If more than 1 item for the SAS is missing, the total score will be set to missing.

Barnes Akathisia Rating Scale Total Score

The total score is the sum of the first 3 items of the BARS. If any item for the BARS (items 1-3) is missing, the total score will be set to missing.

Brief Assessment of Cognition in Schizophrenia Composite Score

BACS includes 6 subtests: verbal memory (0-75), digit sequencing task (0-28), token motor task (0-100), verbal fluency (≥ 0), symbol coding (0-110), and tower of London (0-22). The BACS composite score is an average of the standardized scaled score from each of 6 subtests with sex (male and female) and age group (18-29, 30-39, 40-49, 50-59, and 60-64) adjusted.

Let X_{ij} be the raw score on the test j ($j=1$ to 6) for subject i . Assume that subject i has sex m (1= male and 2 = female) and is in age category n (1= 18-39, 2=40-40, 3=50-59, and 4=60-64 years). The scaled score for subject i on test j is computed as follows:

$$C_{ij} = (X_{ij} - M_{mnj}) / SD_{mnj},$$

where M_{mnj} and SD_{mnj} are the mean and SD for test j , respectively, of the index population for sex m and age category n .

The composite Z score for subject i is calculated as following:

$$Z_i = \frac{\sum_{j=1}^6 C_{ij}}{SD_{mn}},$$

where SD_{mn} is the SD for all tests of the index population for sex m and age category n .

The composite T score for subject i is calculated as $T_i = 10 * Z_i + 50$.

If more than 1 subtest for the BACS is missing, then the composite Z score and T score will be set to missing. LOCF approach will be used to impute missing postbaseline values. Imputation of missing values will be done for the OLTP and the DBTP separately. For the LOCF approach, only the postbaseline total score of a parameter will be imputed; individual item score will not be carried forward. Baseline total score will be carried forward only for the intermittent missing scores immediately after baseline. If all the postbaseline values are missing, baseline value will not be carried forward.

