4.6 Randomization Criteria

Randomization requirements are:

- Ability to safely tolerate cariprazine 4.5 mg/d
- Maintenance of response threshold criteria for 8 weeks following attainment of stability:
 - PANSS total score ≤ 60 ; and
 - $\geq 20\%$ decrease in PANSS total score from Visit 2/Baseline; and

- Score of ≤ 4 on each of the following 7 PANSS items:
 - P1: delusions
 - P2: conceptual disorganization
 - P3: hallucinatory behavior
 - P6: suspiciousness/persecution
 - P7: hostility
 - G8: uncooperativeness
 - G14: poor impulse control; and
- CGI-S ≤ 4

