10.0 EFFICACY ANALYSES

All efficacy analyses for the OLTP will be performed using the OL ITT population, unless stated otherwise. Baselines for efficacy parameters in the OLTP will be defined as the last non-missing efficacy assessment before the first dose of OL IP.

All efficacy analyses for the DBTP will be performed using the DB ITT population, unless stated otherwise. Baselines for the additional efficacy parameters in the DBTP will be defined as the last nonmissing efficacy assessment before the first dose of DB IP.

All statistical tests will be 2-sided hypothesis tests performed at the 5% level of significance and all confidence intervals (CIs) will be 2-sided 95% CIs, unless stated otherwise.

To accommodate the flexible duration of the OLTP, the derived visits in the DBTP will be named as Week *i* post randomization (or DB Week *i*) for a specific Week *i* after the first dose of the DB study medications. The total exposure to IPs for patients in Week *i* post randomization will vary because of the flexible OLTP. The detailed week-mapping windows is provided in Section 16.1.

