10.3 ADDITIONAL EFFICACY PARAMETERS

The additional efficacy parameters will include the following at scheduled postbaseline visits:

- Change from baseline in the PANSS total score
- Change from baseline in PANSS positive subscale score
- Change from baseline in PANSS negative subscale score
- Change from baseline in PANSS factor score for positive symptoms
- Change from baseline in PANSS factor score for negative symptoms
- Percentage response (PANSS improvement \geq 30%)
- Change from baseline in the CGI-S score
- Clinical Global Impressions—Improvement (CGI-I) score

- Change from baseline in the Brief Assessment of Cognition in Schizophrenia scale (BACS) individual subtest scores
- Change from baseline in BACS composite score Z score
- Change from baseline in the BACS composite T score
- Change from baseline in personal and social performance (PSP) score and sub-domain scores

For the continuous endpoints, the change from baseline refers to the change from OL baseline during the OLTP, and the change from DB baseline during the DBTP, unless stated otherwise. For CGI-I, the OL baseline CGI-S value will be used as the baseline variable.

Descriptive statistics for additional quantitative parameters will be provided by visit for the OL ITT population and the DB ITT population using both last-observation-carried forward (LOCF) and observed cases (OC) approaches. LOCF approach will be used to impute missing postbaseline values. Imputation of missing values will be done for the OLTP and the DBTP separately.

For the DBTP, the continuous variables (change from DB baseline) will be analyzed by using a mixed-effects model for repeated measures (MMRM) with treatment group, country, visit, and treatment group-by-visit interaction as fixed effects and the baseline value and baseline-by-visit interaction as the covariates. An unstructured covariance matrix will be used. The Kenward-Roger approximation ([Kenward and Roger, 1997](#)) will be used to estimate denominator degrees of freedom. The analysis will be performed based on post-DB baseline scores using only the OC without imputation of missing values. Least squares mean and their standard errors based on the MMRM analysis will be plotted by treatment group and visit.

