Within regions, countries will be ranked on number of patients that are part of the ITT population and lowest ranked countries will be pooled (sequentially, ie, a new ranking is made after each step) until the smallest pooled country has reached at least 2 patients in each arm.

Additional categorical efficacy parameters will be analyzed in the following way:

Rates for categorical parameters (response) will be reported by treatment group and by visit for both the OLTP and the DBTP (with LOCF imputation). For the DBTP, logistic regression model (with LOCF imputation) will be used to model the probability of a response or the probability of a response as a function of a treatment group and the corresponding baseline score as explanatory variables.

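### Under the general baseline rule, double-blind PANSS response is a 30% fall from a score already at 60 or less: unattainable at 42 or below, and unable to show retained response

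*SAP*

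**What the plan says.** SAP 16.2 defines the responder without naming a baseline: "PANSS responder is defined as patients with 30% or more improvement in PANSS total score relative to baseline". Percentage response is listed in SAP 10.3 and Protocol 7.2.3 as an additional efficacy parameter.

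The baseline for such parameters is set by a general rule in SAP 10.0, repeated in Protocol 7.3: "Baselines for the additional efficacy parameters in the DBTP will be defined as the last nonmissing efficacy assessment before the first dose of DB IP". SAP 10.3 adds a sentence that opens "For the continuous endpoints, the change from baseline refers to the change from OL baseline during the OLTP" and goes on to assign the DB baseline to the DB period. Its wording covers continuous endpoints only. The one parameter that SAP 10.3 expressly ties to the open-label (OL) baseline is CGI-I, which takes the OL CGI-S score as its baseline variable.

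Response is analysed in the DB period. Rates are given by arm and visit with LOCF, and "For the DBTP, logistic regression model (with LOCF imputation) will be used to model the probability of a response", with treatment and "the corresponding baseline score as explanatory variables". Protocol 7.3.3 says the same.

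Entry to the DB period requires "Maintenance of response threshold criteria for 8 weeks following attainment of stability" (Protocol 4.6). This includes a PANSS total of 60 or less and a fall of at least 20% from Visit 2. Protocol 4.5 allows no excursion at Visit 13.

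**The concern.** In a randomised-withdrawal trial, patients enter the DB period already improved, and the question is whether they stay so. A responder rule that demands a further 30% fall from that improved score asks something else. A patient whose PANSS total does not move for 26 weeks is a non-responder at every visit, and so is a patient who relapses on the PANSS total criterion. The two outcomes that the design exists to separate get the same code.

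The scale floor adds a second problem. For part of the permitted baseline range the outcome is fixed at non-response whatever happens. The baseline score is also the covariate in the logistic model, so below a certain covariate value no response can occur.

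At stake is whether a table of DB response rates by arm could be interpreted if it were produced.

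**Working it through.** The documents state no figure for this point, so there is none to reproduce.

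**Inputs**
- PANSS total is the sum of 30 items (SAP 16.2), each scored 1 to 7 (Protocol 6.2.1.1). The minimum is 30 × 1 = 30.
- Neither document subtracts 30 when it takes a percentage.
- The highest DB baseline for a patient randomised per protocol is 60 (Protocol 4.5 and 4.6).
- OL baseline lies between 70 and 120 (Protocol 4.3).

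**Attainability from the DB baseline.** From baseline B, a 30% fall needs a score of 0.7B or less. This is possible only if 0.7B ≥ 30, so B ≥ 30/0.7 = 42.86.

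| DB baseline | 0.7 × B | Largest possible fall | Response needs |
|---|---|---|---|
| 40 | 28.0 | 10/40 = 25.0% | impossible |
| 42 | 29.4 | 12/42 = 28.6% | impossible |
| 43 | 30.1 | 13/43 = 30.2% | exactly 30 |
| 44 | 30.8 | 14/44 = 31.8% | exactly 30 |
| 45 | 31.5 | 15/45 = 33.3% | 31 or less |
| 50 | 35.0 | 20/50 = 40.0% | 35 or less |
| 60 | 42.0 | 30/60 = 50.0% | 42 or less |

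Totals 30 to 42 are 13 of the 31 whole-number values from 30 to 60. That counts scale values, not patients. Prorating for up to three missing items (SAP 16.2) does not help, because a prorated total also has a minimum of 30.

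**Same rule from the OL baseline.** The highest score allowed at randomisation is the smaller of 60 and 0.8B. The raw cut-off is 0.7B. If 30 is subtracted from the denominator, the cut-off is B − 0.3(B − 30) = 0.7B + 9.

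| OL baseline | Highest score at randomisation | Raw cut-off | Cut-off with 30 subtracted |
|---|---|---|---|
| 70 | 56 | 49.0 | 58.0 |
| 75 | 60 | 52.5 | 61.5 |
| 85 | 60 | 59.5 | 68.5 |
| 86 | 60 | 60.2 | 69.2 |
| 100 | 60 | 70.0 | 79.0 |
| 120 | 60 | 84.0 | 93.0 |

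With the raw percentage, a patient randomised at 60 is sure to start as a responder only if the OL baseline is 86 or more. With 30 subtracted, every eligible patient starts as a responder. The smallest improvement occurs at OL baseline 75 and score 60: (75 − 60)/(75 − 30) = 15/45 = 33.3%.

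**Relapsed patients under the OL baseline.** Take an OL baseline of 100.
- A patient randomised at 60 who relapses at 78 (60 × 1.3) is still under the cut-off of 79 when 30 is subtracted.
- A patient randomised at 45 who relapses at 55 (a 10-point rise) is under both cut-offs, 70 and 79.

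Relapse ends participation in the DB period (Protocol 8.9), so LOCF would carry either patient forward as a responder. Changing the baseline alone is not enough.

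**The case against.** **The baseline is not named.** SAP 16.2 says only baseline, the OL/DB sentence in SAP 10.3 is limited to continuous endpoints, and the logistic covariate is just the corresponding score. This stands as a limit on certainty. The general rule in SAP 10.0 still covers all additional parameters in the DB period, and only CGI-I is given an OL baseline. The DB reading is therefore the one the text supports. If the OL baseline was intended, the SAP needs to say so.

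**Sparse data.** A reader might infer that rates will be close to zero in every arm and that the logistic model will fail. The documents do not support this. They give no DB-baseline distribution, so the share of patients at 42 or below could be anywhere from 0 to 100%.

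**Maintenance is measured elsewhere.** A reader might also infer that the trial cannot assess maintenance. It can: time to first relapse is the primary endpoint, and change in PANSS total from DB baseline is modelled over time. The fault lies in this one endpoint.

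**An OL-baseline rule starts at or near 100% responders and can keep relapsed patients as responders.** A high starting rate is what a retained-response endpoint should have. The point about relapsed patients stands and has to be handled in the definition.

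**Subtracting 30 departs from the plan's other PANSS percentages.** The 20% response threshold and the 30% relapse criterion are written without it. This stands, so the subtraction is optional.

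**The analysis may never be run.** The study was terminated early, and SAP Appendix IV keeps the primary analysis, PANSS total change and the BACS composite. Response is not listed. This stands and limits the importance of the point.

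**Conclusion.** The point holds as a minor one. Read with the general baseline rule, DB response cannot occur from a DB baseline of 42 or below. It needs the scale minimum at 43 or 44, and a further 18-point fall at the ceiling of 60. A stable patient is always a non-responder, so neither the rates nor the logistic model can show retained response.

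This rests on three things: the general rule in SAP 10.0 and Protocol 7.3 applies to response, percentages are taken on the raw score, and patients meet the 60-point limit at Visit 13. That stable patients are non-responders does not depend on the baseline distribution; the degree of sparseness does, and cannot be computed from the documents.

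Use of the same rule in the OL period, from baselines of 70 to 120, is not affected by the floor. Response plays no part in the primary analysis or the multiplicity procedure, so no confirmatory conclusion changes.

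**What to change.** In SAP 16.2 and 10.3:
- Define response in the DB period as a 30% or greater improvement in PANSS total from the OL (Visit 2) baseline.
- Name the OL baseline PANSS total as the covariate in the DB logistic model.
- Count a patient who has met the relapse criteria as a non-responder from that visit on, so that LOCF cannot carry a relapsed patient forward as a responder.
- State whether 30 is subtracted from the denominator. Subtracting it makes every eligible patient a responder at randomisation. The raw percentage matches the plan's other PANSS percentages but lets some patients start as non-responders.

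Add an entry to SAP 17.0, because Protocol 7.2.3, 7.3 and 7.3.3 carry the same endpoint, baseline rule and model.

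The cost is wording plus a small change to the derivation program. All the data are already collected. If only the abbreviated report is produced, the change has little practical effect, but it prevents an uninterpretable table if the analysis is run or the definition is reused.

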16.3 REPEATED OR UNSCHEDULED ASSESSMENTS OF SAFETY PARAMETERS

If a patient has repeated assessments before the start of OLTP, the results from the final non-missing assessment made before the start of the OL IP will be used as OL baseline. If end-of-study assessments are repeated or if unscheduled visits occur, the last non-missing postbaseline assessment will be used as the end-of-study assessment for generating summary statistics. However, all postbaseline assessments will be used for PCS value determinations, and all assessments will be presented in the data listings.

16.4 MISSING DATE OF THE LAST DOSE OF INVESTIGATIONAL PRODUCT

When the date of the last dose of OL IP is missing for a patient in the OL Phase Safety Population, all efforts should be made to obtain the date from the Investigator. When the date of the last dose of DB IP is missing for a patient in the DB Safety Population, all efforts should be made to obtain the date from the Investigator. If after all efforts are made it is still missing, the last *available dosing record date* during the corresponding period will be used as the last dose date for the corresponding period.

16.5 MISSING SEVERITY ASSESSMENT FOR ADVERSE EVENTS

If severity is missing for an AE that started before the date of the first dose of OL IP, an intensity of mild will be assigned. If severity is missing for an AE that started on or after the date of the first dose of OL IP, an intensity of severe will be assigned. The imputed values for severity assessment will be used for the incidence summary; the values will be shown as missing in the data listings.

16.6 MISSING CAUSAL RELATIONSHIP TO INVESTIGATIONAL PRODUCT FOR ADVERSE EVENTS

If the causal relationship to the IP is missing for an AE that started on or after the date of the first dose of OL IP, a causality of yes will be assigned. The imputed values for causal relationship to OL or DB treatment will be used for the incidence summary; the values will be shown as missing in the data listings.

16.7 MISSING DATE INFORMATION FOR ADVERSE EVENTS

The following imputation rules only apply to cases in which the start date for AEs is incomplete (ie, partly missing).

Missing month and day

- If the year of the incomplete start date is the same as the year of the first dose of OL IP, the month and day of the first dose of open-label IP will be assigned to the missing fields
- If the year of the incomplete start date is before the year of the first dose of open-label IP, *December 31* will be assigned to the missing fields
- If the year of the incomplete start date is after the year of the first dose of open-label IP, *January 1* will be assigned to the missing fields

Missing month only

- If only the month is missing, the day will be treated as missing and both the month and the day will be replaced according to the above procedure

Missing day only

- If the month and year of the incomplete start date are the same as the month and year of the first dose of open-label IP, the day of the first dose of open-label IP will be assigned to the missing day
- If either the year of the incomplete start date is before the year of the date of the first dose of OL IP or if both years are the same but the month of the incomplete start date is before the month of the date of the first dose of OL IP, the last day of the month will be assigned to the missing day
- If either the year of the incomplete start date is after the year of the date of the first dose of OL IP or if both years are the same but the month of the incomplete start date is after the month of the date of the first dose of OL IP, the first day of the month will be assigned to the missing day

If the stop date is complete and the imputed start date as above is after the stop date, the start date will be imputed by the stop date.

If the start date is completely missing and the stop date is complete, the following algorithm will be used to impute the start date:

- If the stop date is after the date of the first dose of OL IP, the date of the first dose of OL IP will be assigned to the missing start date
- If the stop date is before the date of the first dose of OL IP, the stop date will be assigned to the missing start date

16.8**MISSING DATE INFORMATION FOR PRIOR OR CONCOMITANT MEDICATIONS**

For prior or concomitant medications, including rescue medications, incomplete (ie, partly missing) start dates and/or stop dates will be imputed. When the start date and the stop date are both incomplete for a patient, the start date will be imputed first and then the stop date will be imputed. If the imputed start date is after the imputed stop date, the imputed stop date will be equal to the imputed start date.

